## 1 Protocol Synopsis

PROTOCOL TITLE: A CONTROLLED, PARALLEL-GROUP, RANDOMIZED, OPEN-LABEL STUDY TO EVALUATE TWO LENALIDOMIDE DOSE REGIMENS WHEN USED IN COMBINATION WITH LOW DOSE DEXAMETHASONE FOR THE TREATMENT OF SUBJECTS WITH RELAPSED MULTIPLE MYELOMA	
PROTOCOL NUMBER:	RV
DATE PROTOCOL FINAL:	9-17-2009
STUDY DRUG:	Revlimid®, lenalidomide
INDICATION:	15 mg and 25 mg of lenalidomide in conjunction with low dose dexamethasone
STUDY PHASE:	II

BACKGROUND AND RATIONALE: Several studies have shown that combination chemotherapy with addition of other alkylating agents such as cyclophosphamide or nitrosureas and anthracyclines does not improve the prognosis of subjects with multiple myeloma beyond results obtained with standard MP (Oken, 1994; Oken, et al. 1997). Notably, the median survival of subjects who achieve stable disease (lack of disease progression) is similar to that in subjects who respond to therapy and is superior to survival in subjects whose disease progresses (49 months versus 48 months versus 15 months) (Durie and Salmon, 1975). A recent trial conducted by Eastern Cooperative Oncology Group (ECOG) compared MP therapy to the combination treatment regimen of vincristine, carmustine, melphalan, cyclophosphamide, and prednisone (VBMCP) (Oken, et al. 1997). Although VBMCP resulted in a 72% objective response compared to 52% for MP, the median survivals of both Cohorts were not different. Interferon (IFN), either as part of induction treatment or as maintenance therapy, is only of marginal benefit (Ludwig, et al. 1995). Although subjects with progressive disease despite initial therapy or those who become resistant to initial therapy have a 50 to 75% response to salvage regimens such as vincristine, doxorubicin, and dexamethasone (VAD) (Barlogie, et al. 1984; Monconduit, et al. 1986), these responses are usually of short (months) duration. Myeloma, therefore, remains universally fatal, and the median survival of affected subjects is 3 to 4 years.
 
The primary rationale is to utilize Revlimid at dose that will be well tolerated and effective. We propose to use the need for dose reduction as a criterion to judge tolerability from various causes. In the veteran population which predominantly is in the older age category with number of co-morbidities, a lower dose regimen may be safer and advantageous. In a recent multi-institutional study, the 009 and 010 studies, patients were randomized to receive Revlimid with dexamethasone versus dexamethasone alone. A logistic regression was performed using dose reduction (i.e., whether or not having any lenalidomide dose reduction as the dependent variable). Treatment-emergent neutropenia and thrombocytopenia were the causes of the majority of dose reductions. Predictors analyzed included: age, prior transplant (yes vs. no), high vs. low risk (disease stage variable), previous thalidomide exposure (yes vs. no), previous lines of therapy (<=2 vs. 3+), prior medical history of neutropenia or thrombocytopenia. Among the 353 patients in the Revlimid/Dexamethasone groups, 131 (37.1%) had at least one dose reduction of
	


Revlimid. Age, whether used as a continuous variable or dichotomized one (<math>\leq 65</math> vs. 66+), was the single significant predictor for dose reduction; 46% of the patients aged 66 or older required at least one dose reduction, as compared to 31% of the patients aged 65 or younger. Of interest, when the elderly population was specifically examined, the outcomes were similar for response rate, time to progression and overall survival than the younger group, suggesting that dose reduction had no significant effect on efficacy.
	

STUDY OBJECTIVES:
 
Primary:
 
 
The primary objective of the study is to evaluate the frequency of dose reductions in two different lenalidomide dose regimens.
 
 
Secondary:
 
Secondary objectives are to:
 
 
Evaluate the efficacy of two different lenalidomide dose regimens in patients with multiple myeloma using the EBMT and IMWG criteria.
 
Evaluate the duration of response of 15 mg Lenalidomide and 25 mg of Lenalidomide when used in combination with Low Dose Dexamethasone.
 
Evaluate the safety of 15 mg and 25 mg of Lenalidomide regimens when in combination with dexamethasone.
 
Explore blood and cellular levels of angiogenic factors, cytokines, and adhesion molecules.
 
	

STUDY DESIGN:
 
This is a multi-center, controlled, open-label, randomized (1:1) parallel group study intended to select a tolerable dose regimen with acceptable efficacy of lenalidomide, when used in combination with dexamethasone.
 
Subjects will receive either oral lenalidomide 25 mg once daily for days 1-21 out of a 28 cycle or lenalidomide 15 mg once daily for 1-21 of a 28 day cycle. Subjects will be assessed before the start of treatment, and every 4 weeks while on therapy. Subjects will also receive 40 mg of dexamethasone once a week, (days 1,8,15, 22), and ASA (81 or 325 mg) will be given daily for anticoagulation prophylaxis. Lenalidomide will be reduced if patients develop grade 3 or greater toxicities. If patient has progressive disease after 2nd cycle, then the patient will be taken off the study. If at least a minimal response (MR) has not resulted after cycle 4 then the patient will be taken off the study. (see Section 5.7). Subjects who continue to show evidence of myeloma response will remain on the study and will be evaluated every 4 weeks for response and/or progression.
	

STUDY ENDPOINTS
 
Primary:
 
 
Type, frequency, severity and timing of adverse events and their relationship to combination therapy with lenalidomide plus dexamethasone
 
 
Secondary:
 
 
Duration of M-Protein response during combination therapy with lenalidomide plus dexamethasone
 
Confirmed M-Protein response
 
Expression of angiogenic factors, cytokines, adhesion molecules, and myeloma biomarker expression
 
	

STUDY DURATION: Subjects who respond to lenalidomide plus dexamethasone may continue on therapy until there is evidence of
	
TOTAL SAMPLE SIZE: Approximately 80 subjects will be enrolled.

Lenalidomide (Revlimid®)

progression or unacceptable toxicity. All subjects will be followed for survival indefinitely.
	

DOSING REGIMEN(S): Depending on lenalidomide treatment assignment, subjects will receive either 15 mg p.o. q.d. or 25 mg p.o. q.d. for days 1-21 of a 28 day cycle.. In addition, dexamethasone (40 mg) will be added once a week (Days 1, 8, 15 and 22) to the Lenalidomide regimen, with a dose reduction on the same schedule if the patient cannot tolerate the higher dose of dexamethasone. ASA (81 or 325mg) will be given daily for anticoagulation prophylaxis.
	
STUDY DRUG SUPPLIES: Celgene Corporation will supply lenalidomide as 5 mg and 25 mg capsules.

## 2 Schedule of Study Assessments \*

Procedure	Screening ≤ 14 days from Baseline (First day study drug administration)	Cycle 1				 Cycles 2, 4, 6, 8+	 Cycles 3, 5, 7, 9+	Discontinuation From Study Drug
		Day 1	Day 8	Day 15	Day 22	Day 1	Day 1	
Record prior medications, treatments	X							
Record prior anti-cancer therapies	X							
Physical examination, vital signs	X	X				X	X	X
Weight	X							
ECOG performance status	X							
Chest x-ray 	X 							X 
ECG	X							
Register patient for RevAssist® 	X							
Pregnancy testing 	X 	X	X	X	X	X 	X 	X 
Education and counseling checklist 	X 	X 				X 	X 	
Skeletal Survey	X							X
Hematology • CBC, differential, platelets	X	X	X	X	X	X	X	X
Serum chemistry • Electrolytes, BUN, glucose, creatinine • Liver profile : SGOT, SGPT, alkaline phosphatase, total bilirubin, total protein, albumin • Calcium • CrCl ≥ 40 ml/min • Amylase ≤ 2.5x upper limit of normal	X X X X X	X X X X X	X X X X X	X X X X X	X X X X X	X X X X X	X X X X X	X X X X X
Multiple Myeloma Disease Assessment: • β 2 -microglobulin, C-reactive protein  • Serum protein electrophoresis with quantitated M-protein and Freelite	X  X					X	X	X
Serum Secretors: • Quantitative immunoglobulins • Serum immunofixation	X X					X X	X X	X X
Urine Secretors: • 24hr Urine total protein and urine protein electrophoresis and urine freelite • Immunofixation from 24hr urine	X  X 					X  X 	X  X 	X  X 

Procedure	Screening ≤ 14 days from Baseline (First day study drug administration)	Cycle 1				 Cycles 2, 4, 6, 8+	 Cycles 3, 5, 7, 9+	Discontinuation From Study Drug
		Day 1	Day 8	Day 15	Day 22	Day 1	Day 1	
Non-secretors: • Freelite™ • Bidimensional measurement of soft tissue plasmacytomas if present 	X X					X X 	X X 	X X 
Bone marrow aspirate and biopsy • Cytogenetics  • Morphology	X  X							X 
HIV Test	X							
Hep A,B,C titers (HAV, HBV, HCV)	X							
Dispense Cycle 1 study drug		X						
Response assessment 						X 	X 	X
Record adverse events		X	X	X	X	X	X	X
Record concomitant meds/procedures		X				X	X	X
Dispense study drug for next cycle					X	X	X	
Perform drug accountability					X	X		X

\* An unscheduled visit can occur at any time during the study. Source must be maintained for these unscheduled visits. The date for the visit and any data generated must be recorded on the appropriate CRF. Source documents for these unscheduled visits must also be maintained.

 Not needed if Chest CT scan has been obtained.

 Pregnancy tests for females of childbearing potential. A female of childbearing potential (FCBP) is a sexually mature female who: 1) has not undergone a hysterectomy or bilateral oophorectomy; or 2) has not been naturally postmenopausal for at least 24 consecutive months (i.e., has had menses at any time in the preceding 24 consecutive months).

 Pregnancy tests must occur 10 – 14 days and again within 24 hours prior to initiation of lenalidomide. FCBP with regular or no menstruation must have a pregnancy test weekly for the first 4 weeks and then every 28 days while on therapy (including breaks in therapy); at discontinuation of lenalidomide and at Day 28 post the last dose of lenalidomide. Females with irregular menstruation must have a pregnancy test weekly for the first 4 weeks and then every 14 days while on therapy (including breaks in therapy), at discontinuation of lenalidomide and at Day 14 and Day 28 post the last dose of lenalidomide (see Appendix A: Risks of Fetal Exposure, Pregnancy Testing Guidelines and Acceptable Birth Control Methods). All counseling will be done through RevAssist®

 Patients are required to complete counseling every 28 days during treatment with lenalidomide, follow the pregnancy testing and birth control requirements of the program that are appropriate for the patient and take telephone surveys regarding compliance with the program.

 Mandatory at the beginning and end of study

 Repeat every cycle only if protein present in urine at screening and/or 24hr IFE is positive.

 Repeat to verify response for response assessment and q 2 months and/or as clinically indicated for follow-up

 Cytogenetics only at screening; do not repeat if information available from an earlier bone marrow biopsy. (BMB).

 Repeat as clinically indicated or to confirm CR.

 If patient has progressive disease after 2nd cycle, then the patient will be taken off the study. If at least a minimal response (MR) has not resulted after cycle 4, then the patient will be taken off the study. Subjects who continue to show evidence of myeloma response will remain on the study and will be evaluated every 4 weeks for response/progression.

---

 All patients enrolled in the study must register through RevAssist® and must comply with all requirements of the RevAssist® program. Prescriptions must be filled within 7 days for females of childbearing potential and 14 days for all other risk categories. Drug will be shipped on a per patient basis by the contract pharmacy to the clinic site. Only enough lenalidomide for one cycle of therapy will be supplied to the patient each cycle.

 **All subjects who respond to lenalidomide plus dexamethasone may continue on therapy until there is evidence of progression or unacceptable toxicity. All subjects will be followed for survival indefinitely.**

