## **5.3 Visit schedule and assessments**

Screening Assessments and all on study scheduled visits and assessments are outlined in Section 2 Table of Study Assessments.

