**Criteria for Response**

Requires all of the following:

- Disappearance of the original monoclonal protein from the blood and urine on at least two determinations for a minimum of six weeks by immunofixation studies
- < 5% plasma cells in the bone marrow on at least one determination
- No increase in the size or number of lytic bone lesions (development of a compression fracture does not exclude response)
- Disappearance of soft tissue plasmacytomas for at least six weeks.

Near CR

- Requires all of above except immunofixation remains positive
- Or normal FLC ratio

Partial Response (PR)

Requires all of the following:

- $\geq 50\%$  reduction in the level of serum monoclonal protein for at least two determinations six weeks apart
- If present, reduction in 24-hour urinary light chain excretion by either  $\geq 90\%$  or to < 200 mg for at least two determinations six weeks apart
- $\geq 50\%$  reduction in the size of soft tissue plasmacytomas (by clinical or radiographic examination) for at least six weeks
- No increase in size or number of lytic bone lesions (development of compression fracture does not exclude response)
- If the serum and urine M-protein are unmeasurable a  $\geq 50\%$  decrease in the difference between involved and uninvolved FLC levels is required in place of the M-protein criteria

Minimal Response (MR)

Requires all of the following:

- $\geq 25\%$  to  $\leq 49\%$  reduction in the level of serum monoclonal protein for at least two determinations six weeks apart
- If present, a 50 to 89% reduction in 24 hour light chain excretion, which still exceeds 200 mg/24hr, for at least two determinations six weeks apart.
- For patients with non-secretory myeloma only, a 25 to 49% reduction in plasma cells in the bone marrow for a minimum of six weeks
- no increase in size or number of lytic bone lesions (development of compression fracture does not exclude response)

Stable Disease

Not meeting the criteria for CR, PR or PD

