**Criteria for Response**

Requires one or more of the following:

- > 25% increase in the level of serum monoclonal paraprotein, which must also be an absolute increase of at least 5G/dL and confirmed on a repeat investigation
- > 25% increase in 24-hour urinary light chain excretion, which must also be an absolute increase of at least 200 mg/24hours and confirmed on a repeat investigation
- > 25% increase in plasma cells in a bone marrow aspirate or on trephine biopsy, which must also be an absolute increase of at least 10%
- Only in patients without measurable serum and urine M-protein levels: the difference between involved and uninvolved FLC levels (absolute increase must be <10mg/L)
- Definite increase in the size of existing lytic bone lesions or soft tissue plasmacytomas or definite development of new bone lesions or soft tissue plasmacytomas
- Development of hypercalcemia (corrected serum calcium > 11.5 mg/dL or 2.8 mmol/L not attributable to any other cause)

Relapse from CR

Requires at least one of the following:

- Reappearance of serum or urinary paraprotein on immunofixation or routine electrophoresis confirmed by at least one follow-up and excluding oligoclonal immune reconstitution
- $\geq$  5% plasma cells in the bone marrow aspirate or biopsy
- Development of new lytic bone lesions or soft tissue plasmacytomas or definite increase in the size of residual bone lesions (not including compression fracture).
- Development of hypercalcemia (corrected serum calcium > 11.5 mg/dL or 2.8 mmol/L not attributable to any other cause).

**\*Note clarification to IMWG criteria for coding CR and VGPR in patients in whom the only measurable disease is by serum FLC levels:** CR in such patients a normal FLC ratio of 0.26-1.65 in addition to CR criteria listed above. VGPR in such patients is defined as a >90% decrease in the difference between involved and uninvolved free light chain FLC levels.

Based on the criteria for evaluating disease response and progression in patients with multiple myeloma treated by high-dose therapy and haemopoietic stem cell transplantation. Myeloma Subcommittee of the EBMT. European Group for Blood and Marrow Transplant. Br J Haematol. 102: 1998; 1115-1123. and International Myeloma Working Group. Criteria for the classification of monoclonal gammopathies, multiple myeloma and related disorders: a report of the International Myeloma Working Group. Br J Haematol 2003; 121: 749–757.

**10.1**      Time to Treatment Failure

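### Section 2 schedules plasmacytoma measurement only for non-secretors, although Appendix C uses plasmacytoma change to define CR, PR and progression whatever the secretory status

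*Combined protocol and SAP*

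**What the plan says.** **Schedule.** In Section 2 the item "Bidimensional measurement of soft tissue plasmacytomas if present" appears once, in the block headed for non-secretors. It is marked at screening, on Day 1 of the later cycles and at discontinuation. Footnote 7 to that row sets only when the measurement is repeated. Section 5.3 says that screening assessments and "all on study scheduled visits and assessments are outlined in Section 2", so there is no second list to fill a gap.

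**Criteria.** Appendix C defines CR and PR as sets of items that must all be met. CR includes "Disappearance of soft tissue plasmacytomas for at least six weeks". PR includes at least a 50% "reduction in the size of soft tissue plasmacytomas (by clinical or radiographic examination) for at least six weeks". Progression needs only one item from its list, and one such item is "Definite increase in the size of existing lytic bone lesions or soft tissue plasmacytomas", or the definite appearance of new lesions of either kind. None of these items is limited to non-secretors.

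**Use.** Section 7 sends the interpretation of response to Appendix C. Section 10.3 defines objective response as PR or CR by the EBMT and IMWG criteria, checks whether a one-sided 95% lower limit exceeds 45%, and ends duration of response at progression or death.

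**The concern.** Section 2 tells sites what to collect, and Appendix C says what must be known to classify a patient. For a secretor with a plasmacytoma the first does not supply the second. A percentage reduction needs a recorded baseline size, and growth needs a size to compare with.

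Three things are at stake in these patients:

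- whether PR or CR can be established at all;
- when progression is recognised, and so how long a response is recorded as lasting;
- the on-study decisions that depend on progression (Sections 5.1 and 5.7).

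The likely direction of error is upward. If the plasmacytoma item has not been measured, an assessor may let the M-protein result stand for the whole response, and the plan has no rule for a missing plasmacytoma assessment.

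**Working it through.** The plan states no figure on this point. The check sets its sections side by side and then gives a scale from labelled assumptions.

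**1. What each block of the schedule collects (Section 2)**

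| Block | Content |
|---|---|
| Serum secretors | "Serum Secretors: • Quantitative immunoglobulins • Serum immunofixation" |
| Urine secretors | "Urine Secretors: • 24hr Urine total protein and urine protein electrophoresis and urine freelite • Immunofixation from 24hr urine" |
| Non-secretors | "Non-secretors: • Freelite™ • Bidimensional measurement of soft tissue plasmacytomas if present" |
| All-patient myeloma assessment | β2-microglobulin, C-reactive protein, serum electrophoresis with M-protein and Freelite |

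Only the non-secretor block has a plasmacytoma item.

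**2. Whether Appendix C intends the same restriction.** Where Appendix C restricts an item, it says so. The marrow item under minimal response is confined to non-secretory patients, and the free-light-chain item under progression to patients without measurable serum and urine M-protein. The plasmacytoma items carry no such words.

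**3. Whether the affected patient can be enrolled.** Section 5.2.1.3 admits a patient on serum or urine M-protein, and Section 5.2.2 does not exclude a coexisting plasmacytoma. So yes.

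**4. What else is scheduled for a secretor.** Physical examination takes place at screening, Cycle 1 Day 1, Day 1 of each later cycle and discontinuation. Skeletal survey and chest x-ray (or a chest CT in its place) take place at screening and discontinuation. Nothing tells the site to measure and record a plasmacytoma, and no soft tissue imaging is scheduled between screening and discontinuation. Section 5.2.1.3 itself foresees MRI or CT for such lesions.

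**5. Scale.** The documents do not give the share of patients who are secretors with a plasmacytoma.

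*Patients exposed to the gap.* With an assumed share of 5% to 15%, this is 40 × 0.05 = 2 to 40 × 0.15 = 6 per arm. These are not misclassified patients.

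*Responders misclassified.* Assumptions:

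- M-protein response rate 61%, the lenalidomide plus dexamethasone rate quoted in Section 3.2 (under a more intensive dexamethasone schedule);
- share f of secretors with a plasmacytoma, widened to 5% to 20%;
- share m of M-protein responders among them who fail the plasmacytoma item, 10% to 50%;
- all of these still counted as responders.

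Misclassified per arm = 40 × 0.61 × f × m. Response rate under the full criteria = 0.61 × (1 − f × m).

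| f | m | Misclassified per 40 | Rate under full criteria |
|---|---|---|---|
| 5% | 10% | 0.12 | 60.7% |
| 10% | 25% | 0.61 | 59.5% |
| 20% | 50% | 2.44 | 54.9% |

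*The 45% check.* The exact (Clopper-Pearson) one-sided 95% lower limit for r responders of n is the 5th percentile of Beta(r, n − r + 1).

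| Responders | Lower limit |
|---|---|
| 23/40 | 43.3% |
| 24/40 | 45.8% |
| 43/80 | 44.0% |
| 44/80 | 45.2% |

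Section 10.3 names neither the interval method nor whether the check is per arm or pooled. The Wilson limit first passes 45% at the same counts, 24/40 and 44/80. At 61% the expected count is 40 × 0.61 = 24.4 per arm, next to the per-arm threshold.

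**The case against.** A reader might infer that the plan scores secretors with a plasmacytoma as responders on M-protein alone, the more so because Section 4.2.2 names the secondary endpoint as an M-protein response. The documents do not support that. Appendix C requires every listed item for PR and CR, including no increase in lytic lesions and, for CR, marrow plasma cells below 5%. A halved M-protein with a growing plasmacytoma is progression under Appendix C, and Section 5.7 ties stopping to progression as defined there. What the text leaves is an undetermined classification when the measurement was not taken.

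The other side also has these points:

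- **Clinical examination is accepted.** Appendix C allows size to be judged clinically, and every patient is examined each cycle. This stands for palpable lesions, though nothing requires the size to be recorded. It does not help with lesions seen only on imaging.
- **The headings may not be exclusive.** Freelite appears under non-secretors and again in the all-patient block. But Freelite is listed a second time, and the plasmacytoma item is not. The table was read from a PDF, yet heading and item are adjacent and footnote 7 does not contradict the grouping.
- **The stakes are modest.** This stands. Response is secondary, Section 10.3 says the study is not powered to compare it, and both arms share the schedule, so no between-arm bias is shown. Dependence on one patient is a feature of any threshold on a count and is not evidence of the defect.

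**Conclusion.** Section 2 and Appendix C disagree and must be reconciled. Followed as written, the schedule leaves a required component of CR, PR and progression unrecorded in secretors who have a plasmacytoma. The firm part of the gap is the missing recorded baseline and follow-up size, and lesions that need imaging.

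The consequence is that PR or CR cannot be properly established in these patients and progression may be recognised late, with a risk of overcalled response and longer recorded duration. How many patients this concerns is unknown. The range of 0.1 to 2.4 misclassified responders per arm of 40 rests wholly on the assumed prevalence, discordance and response rate, and on every discordant patient being counted as a responder. It would matter for the 45% check only if the observed count fell close to 24/40 or 44/80.

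The effect is confined to the secondary response, progression and duration endpoints and to on-study decisions that use them. The primary analysis of dose reduction is unaffected.

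**What to change.** 1. In Section 2, move the row out of the non-secretor block into the all-patient disease assessment, labelled *Any patient with a soft tissue plasmacytoma*. Allow clinical or radiographic examination, as Appendix C does, and leave footnote 7 unchanged.
2. In Section 7, state that a patient with a plasmacytoma at baseline is not counted as PR or CR in the response analysis without that assessment. This settles the missing-assessment case, which Appendix C leaves open; it is a rule for the analysis and does not alter treatment decisions.

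If the plasmacytoma items were meant for non-secretors only, Appendix C would have to say so. That would change the response definition rather than the schedule.

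The cost is a wording change, a few additional measurements in a small number of patients, and possibly a slightly lower response rate. The measurements are ones that Appendix C already needs.
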